### 2.3.2. Benefit Assessment

PF-07321332/ritonavir will not provide any clinical benefit to healthy participants in this study. Any anticipated benefit to participants would be in terms of contribution to the process of developing a new therapy in an area of unmet medical need.

### 2.3.3. Overall Benefit/Risk Conclusion

PF-07321332/ritonavir is not expected to provide any clinical benefit to healthy participants in this study. Taking into account the measures taken to minimize risk to participants of this study, the potential risks identified in association with PF-07321332/ritonavir are justified by the anticipated benefits, in terms of contribution to the process of developing a new therapy in an area of unmet medical need.

## 3. OBJECTIVES AND ENDPOINTS

Objectives	Endpoints
Primary: 

To evaluate the effect of a high-fat meal on the exposure of PF-07321332 boosted with ritonavir following a single oral dose of PF-07321332 in combination with ritonavir using 150 mg tablet formulation of PF-07321332.

	Primary: 

The ratio of <math>AUC_{last}</math>, <math>AUC_{inf}</math> (if data permit) and <math>C_{max}</math> of PF-07321332.

Secondary: 

To characterize the pharmacokinetic parameters of PF-07321332 boosted with ritonavir following a single oral dose of PF-07321332 in combination with ritonavir.

To evaluate the safety and tolerability of PF-07321332/ritonavir in healthy participants.

	Secondary: 

<math>T_{max}</math>, and <math>t_{1/2}</math>, <math>CL/F</math> and <math>V/F</math> (if data permit).

Assessment of TEAEs, clinical laboratory abnormalities, vital signs, and 12-lead ECGs.

## 4. STUDY DESIGN

### 4.1. Overall Design

This is a Phase 1, open-label, single dose, randomized, 2-treatment, 2-sequence, 2-period crossover study to evaluate the effect of a high-fat meal on the relative bioavailability of PF-07321332 boosted with ritonavir following single dose oral administration of PF-07321332 in combination with ritonavir using 150 mg tablet formulation of PF-07321332 in healthy adult participants. The study will consist of 2 treatments: a single oral dose of 300 mg PF-07321332 (2 × 150 mg tablets) under fasted conditions and 3 doses of 100 mg ritonavir at -12 hour, 0 hour and 12 hour related to PF-07321332 dosing (Treatment A), and a single oral dose of 300 mg PF-07321332 (2 × 150 mg tablets) under fed conditions and 3 doses of 100 mg ritonavir at -12 hour, 0 hour and 12 hour related to PF-07321332 dosing (Treatment B). There will be a total of 2 treatment sequences shown in [Table 1](#) with the assigned Treatments A or B in each treatment period.

A total of approximately 12 healthy male and/or female participants will be randomly assigned to investigational product such that approximately 6 participants will be enrolled to

each sequence. Participants who withdraw from the study may be replaced at the sponsor's discretion in collaboration with the Investigator.

Each enrolled participant will participate in 2 study periods to receive 2 different treatments according to the sequence determined by randomization:

- Treatment A: Single oral dose of 300 mg PF-07321332 (2 × 150 mg tablets) under fasted conditions and 3 doses of 100 mg ritonavir at -12 hour, 0 hour and 12 hour related to PF-07321332 dosing. (Reference)
- Treatment B: Single oral dose of 300 mg PF-07321332 (2 × 150 mg tablets) under fed conditions and 3 doses of 100 mg ritonavir at -12 hour, 0 hour and 12 hour related to PF-07321332 dosing. (Test)

Participants will be randomly assigned to 1 of 2 sequences as in Table 1. Serial PK samples will be collected at timepoints shown in [SoA](#).

Participants will be discharged on Period 2, following completion of all assessments.

**Table 1. Treatment Sequences**

	Period 1	Washout (4 days between PF-07321332 dosing)	Period 2
Sequence 1 (n=6)	Treatment A		Treatment B
Sequence 2 (n=6)	Treatment B		Treatment A

The total planned duration of participation, from the screening visit to the last Follow-up phone call, is approximately 10 weeks. Participants will be screened within 28 days prior to the first dose of investigational products and if all eligibility criteria are fulfilled, the participants will report to the CRU on Day -1 and will be required to stay in the CRU for 8 days and 7 nights.

Eligible participants will be admitted to the CRU at least 12 hours prior to the dosing of PF-07321332 on Day 1. On the evening of Day -1, participants will receive a single oral dose of ritonavir 100 mg (-12 hour relative to PF-07321332/ritonavir dosing). On the morning of Day 1 of each period, participants will receive a single dose of PF-07321332 300 mg/ritonavir 100 mg as per randomization schedule. Study interventions will be administered with approximately 240 mL of ambient temperature water. In fed periods (Sequence 2, Period 1 and Sequence 1, Period 2), following an overnight fast of at least 10 hours, participants should begin breakfast approximately 30 minutes prior to PF-07321332/ritonavir administration. A high-fat (approximately 50% of total caloric content of the meal), high-calorie (approximately 800 to 1000 calories) breakfast will be consumed over approximately a 20-minute interval with PF-07321332/ritonavir administered within approximately 10 minutes of completion of the meal. Ritonavir, 100 mg, will continue to be dosed at 12 hours post PF-07321332 dosing. Serial PK samples will be collected up to 48 hours post dose. Period 2 will begin on Study Day 4 (referred to as Period 2, Day -1).

Participants will be discharged from the CRU on Period 2, Day 3 following completion of all assessments.

Participants will be confined in the CRU for a total of at least 8 days and 7 nights and discharged at the discretion of the investigator. If a participant has any clinically significant, study related abnormalities at the conclusion of a scheduled inpatient portion of the study, the Pfizer medical monitor (or designated representative) should be notified and the participant may be asked to remain in the CRU until such abnormalities are deemed not clinically significant, or it is safe for outpatient follow-up. A safety follow-up call will be made to participants approximately 28 to 35 days from administration of the final dose of study intervention.

## 4.2. Scientific Rationale for Study Design

The objective of the study is to evaluate the effect of a high-fat meal on the relative bioavailability of PF-07321332 following a single dose oral administration of PF-07321332 in combination with ritonavir using 150 mg tablet formulation of PF-07321332 in healthy adult participants.

The study is being designed as a crossover study to account for any period effect. Between each treatment period, a minimum of 4-day washout is proposed to minimize any residual PF-07321332 concentrations prior to start of the next period, as PF-07321332 has a half-life of approximately 6 to 13 hours when co-administered with ritonavir.

### 4.2.1. Choice of Contraception/Barrier Requirements

Human reproductive safety data are limited for PF-07321332, but there is no suspicion of human teratogenicity based on the intended pharmacology of the compound. Therefore, the use of a highly effective method of contraception is required (see [Appendix 4](#)).

CCI

## 4.3. Justification for Dose

The dose of 300 mg PF-07321332/100 mg ritonavir for 5 days is the intended therapeutic dose and duration to be evaluated in Phase 2/3 studies. This dose is lower than the highest dose evaluated in the Phase 1 study (C4671001) and is expected to be safe and well tolerated.

This study is designed to evaluate the effect of a high-fat meal on the relative bioavailability of PF-07321332 150 mg tablet in healthy adult participants at intended therapeutic dose. Therefore, a single oral dose 300 mg PF-07321332/100 mg ritonavir will be used in this food effect study. To obtain the enough effect of ritonavir as CYP3A4 inhibitor, 100 mg ritonavir will be dosed prior to PF-07321332/ritonavir administration.

#### **4.4. End of Study Definition**

The end of the study is defined as the date of last scheduled procedure shown in the [SoA](#) for the last participant in the trial.

A participant is considered to have completed the study if he/she has completed all periods of the study, including the last scheduled procedure shown in the [SoA](#).

### **5. STUDY POPULATION**

This study can fulfill its objectives only if appropriate participants are enrolled. The following eligibility criteria are designed to select participants for whom participation in the study is considered appropriate. All relevant medical and nonmedical conditions should be taken into consideration when deciding whether a particular participant is suitable for this protocol.

Prospective approval of protocol deviations to recruitment and enrollment criteria, also known as protocol waivers or exemptions, is not permitted.

#### **5.1. Inclusion Criteria**

Participants are eligible to be included in the study only if all of the following criteria apply:

##### **Age and Sex:**

1. Participants  $\geq 18$  years of age, inclusive, at the time of signing the ICD.
  - Refer to [Appendix 4](#) for reproductive criteria for male ([Section 10.4.1](#)) and female ([Section 10.4.2](#)) participants.

##### **Type of Participant and Disease Characteristics:**

2. Male and female participants who are overtly healthy as determined by medical evaluation including medical history, physical examination, laboratory tests, vital signs and 12-lead ECGs.
3. Participants who are willing and able to comply with all scheduled visits, treatment plan, laboratory tests, lifestyle considerations, and other study procedures.
4. Female participants of childbearing potential must have a negative pregnancy test.

##### **Weight:**

5. BMI of 17.5 to 30.5 kg/m^2; and a total body weight  $>50$  kg (110 lb).

### **Informed Consent:**

6. Capable of giving signed informed consent as described in [Appendix 1](#), which includes compliance with the requirements and restrictions listed in the ICD and in this protocol.

### **5.2. Exclusion Criteria**

Participants are excluded from the study if any of the following criteria apply:

#### **Medical Conditions:**

1. Positive test result (RT-PCR) for SARS-CoV-2 infection at the time of screening or Day -1.
2. Evidence or history of clinically significant hematological, renal, endocrine, pulmonary, gastrointestinal, cardiovascular, hepatic, psychiatric, neurological, or allergic disease (including drug allergies, but excluding untreated, asymptomatic, seasonal allergies at the time of dosing).
3. Clinically relevant abnormalities requiring treatment (eg, acute myocardial infarction, unstable ischemic conditions, evidence of ventricular dysfunction, serious tachy- or brady-arrhythmias) or indicating serious underlying heart disease (eg, prolonged PR interval, cardiomyopathy, heart failure, underlying structural heart disease, Wolff Parkinson-White syndrome).
4. Any condition possibly affecting drug absorption (eg, gastrectomy, cholecystectomy).
5. History of HIV infection, hepatitis B, or hepatitis C; positive testing for HIV, HBsAg, or HCVAb. Hepatitis B vaccination is allowed.
6. Other medical or psychiatric condition including recent (within the past year) or active suicidal ideation/behavior or laboratory abnormality or other conditions or situations related to COVID-19 pandemic (eg, contact with positive case, residence, or travel to an area with high incidence) that may increase the risk of study participation or, in the investigator's judgment, make the participant inappropriate for the study.

#### **Prior/Concomitant Therapy:**

7. Use of prescription or nonprescription drugs and dietary and herbal supplements within 7 days or 5 half-lives (whichever is longer) prior to the first dose of study intervention. Refer to [Section 6.8 Concomitant Therapy](#) for additional details.
  - Concomitant use of any medications or substances that are strong inducers of CYP3A4 are prohibited within 28 days prior to first dose of PF-07321332/ritonavir and during study treatment.

8. Current use of any prohibited concomitant medication(s) or those unwilling/unable to use a permitted concomitant medication(s). Refer to [Section 6.8 Concomitant Therapy](#).
9. Participant who have received a COVID-19 vaccine within 7 days before screening or admission, or who are to be vaccinated with a COVID-19 vaccine at any time during the study confinement period.

#### **Prior/Concurrent Clinical Study Experience:**

10. Previous administration with an investigational drug within 30 days (or as determined by the local requirement) or 5 half-lives preceding the first dose of study intervention used in this study (whichever is longer). Participants who have participated in previous clinical trials with PF-07321332 may be eligible to participate in this study as long as they meet all other criteria.

#### **Diagnostic Assessments:**

11. A positive urine drug test.
12. Screening supine BP  $\geq 140$  mm Hg (systolic) or  $\geq 90$  mm Hg (diastolic), following at least 5 minutes of supine rest. If BP is  $\geq 140$  mm Hg (systolic) or  $\geq 90$  mm Hg (diastolic), the BP should be repeated 2 more times and the average of the 3 BP values should be used to determine the participant's eligibility.
13. Baseline standard 12-lead ECG that demonstrates clinically relevant abnormalities that may affect participant safety or interpretation of study results (eg, baseline QTcF interval  $>450$  msec, complete LBBB, signs of an acute or indeterminate-age myocardial infarction, ST-T interval changes suggestive of myocardial ischemia, second- or third-degree AV block, or serious bradyarrhythmias or tachyarrhythmias). If the baseline uncorrected QT interval is  $>450$  msec, this interval should be rate-corrected using the Fridericia method and the resulting QTcF should be used for decision making and reporting. If QTcF exceeds 450 msec, or QRS exceeds 120 msec, the ECG should be repeated 2 more times and the average of the 3 QTcF or QRS values should be used to determine the participant's eligibility. Computer-interpreted ECGs should be overread by a physician experienced in reading ECGs before excluding a participant.
14. Participants with **ANY** of the following abnormalities in clinical laboratory tests at screening, as assessed by the study-specific laboratory and confirmed by a single repeat test, if deemed necessary:
  - AST **or** ALT level  $\geq 1.25 \times$  ULN;
  - Total bilirubin level  $\geq 1.5 \times$  ULN; participants with a history of Gilbert's syndrome may have direct bilirubin measured and would be eligible for this study provided the direct bilirubin level is  $\leq$  ULN.

PFIZER CONFIDENTIAL

- eGFR <90 mL/min/1.73 m^2 with 10% variation based on the CKD-EPI equation.

#### **Other Exclusions:**

15. History of alcohol abuse or binge drinking and/or any other illicit drug use or dependence within 6 months of screening. Binge drinking is defined as a pattern of 5 (male) and 4 (female) or more alcoholic drinks in about 2 hours. As a general rule, alcohol intake should not exceed 14 units per week (1 unit = 8 ounces [240 mL] beer, 1 ounce [30 mL] of 40% spirit or 3 ounces [90 mL] of wine).
16. Use of tobacco or nicotine containing products in excess of the equivalents of 5 cigarettes per day or 2 chews of tobacco per day.
17. Blood donation (excluding plasma donations) of approximately 1 pint (500 mL) or more within 60 days prior to dosing.
18. History of sensitivity to heparin or heparin-induced thrombocytopenia.
19. Unwilling or unable to comply with the criteria in the Lifestyle Considerations section of this protocol.
20. Investigator site staff or Pfizer employees directly involved in the conduct of the study, site staff otherwise supervised by the investigator, and their respective family members.
21. History of sensitivity reactions to ritonavir, or any of the formulation components of PF-07321332 or ritonavir.
22. Pregnant or breastfeeding women.

#### **5.3. Lifestyle Considerations**

The following guidelines are provided:

##### **5.3.1. Meals and Dietary Restrictions**

- Participants must abstain from all food and drink (except water) at least 4 hours prior to any safety laboratory evaluations and 10 hours prior to the collection of the predose PK sample on Day 1 of each Period.
- For the fed periods (Sequence 2, Period 1 and Sequence 1, Period 2) only, the FDA guidance for evaluation of a food effect on bioavailability recommends using meal conditions that are expected to provide the greatest effects on gastrointestinal physiology so that systemic drug availability is maximally affected. Therefore, a high-fat (approximately 50% of total caloric content of the meal), high-calorie (approximately 800 to 1000 calories) meal will be used for the evaluation of a food effect in this study. The provided meal will be similar in composition to the meal referenced in the FDA guidance on food-effect bioavailability and fed bioequivalence

studies. On Day 1 of the fed periods (Sequence 2, Period 1 and Sequence 1, Period 2), following an overnight fast of at least 10 hours, participants should begin breakfast approximately 30 minutes prior to PF-07321332/ritonavir administration. The breakfast will be consumed over approximately a 20-minute interval with PF-07321332/ritonavir administered within approximately 10 minutes of completion of the meal. Participants will be encouraged to complete the entire breakfast. There are no water restrictions prior to and after dosing.

- For the fasted periods (Sequence 1, Period 1 and Sequence 2, Period 2), water is permitted until 1 hour prior to study intervention administration. Water may be consumed without restriction beginning 1 hour after dosing. Noncaffeinated drinks (except grapefruit or grapefruit-related citrus fruit juices—see below) may be consumed with meals and the evening snack.
- Lunch will be provided approximately 4 hours after PF-07321332/ritonavir dosing.
- Dinner will be provided approximately 30 minutes prior to ritonavir administration at -12 hours and 12 hours. The dinner will be consumed over approximately a 20-minute interval with ritonavir administered within approximately 10 minutes of completion of the meal.
- An evening snack may be permitted.
- Participants will refrain from consuming red wine, grapefruit, or grapefruit-related citrus fruits (eg, Seville oranges, pomelos, fruit juices) from 7 days prior to the first dose of study intervention until collection of the final PK blood sample.
- While participants are confined, their total daily nutritional composition should be approximately 55% carbohydrate, 30% fat, and 15% protein. The daily caloric intake per participant should not exceed approximately 3200 kcal during the fasting periods of the study.

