### 1.3. Schedule of Activities

The SoA table provides an overview of the protocol visits and procedures. Refer to the **STUDY ASSESSMENTS AND PROCEDURES** section of the protocol for detailed information on each procedure and assessment required for compliance with the protocol.

The investigator may schedule visits (unplanned visits) in addition to those listed in the SoA table, in order to conduct evaluations or assessments required to protect the well-being of the participant.

Visit Identifier Abbreviations used in this table may be found in Appendix 8	Screening a	Periods 1-2 b													28-35 days (Follow-Up)	Early Termination/Discontinuation	
		Day -1	Day 1														
Days Relative to Day 1	Days -28 to -2	0	0.5	1	1.5	2	2.5	3	4	6	8	12	16	24	48		
Hours After Dose																	
Informed consent	X																
CRU Confinement c		X	→	→	→	→	→	→	→	→	→	→	→	→	X		
Inclusion/exclusion criteria	X	X u															
Medical/medication history (update) d	X	X u															
Demography e	X																
Physical exam f	X	X u															
Safety laboratory (including aPTT, PT-INR, Fibrinogen, and eGFR) g	X	X u												X		X	
FSH h	X																
Urine drug testing i	X	X u															
Serology: HBsAg, HBsAb, HBcAb, HCVAb, and HIV j	X																
Pregnancy test (WOCBP only)	X	X u												X		X	
Contraception check k	X	X u													X		
Single supine 12-lead ECG l	X		X v											X		X	
Vital signs (BP/PR/RR/temperature) m	X		X v											X		X	
COVID-19 questionnaire n	X	X u															

PFIZER CONFIDENTIAL

Visit Identifier Abbreviations used in this table may be found in Appendix 8	Screening a	Periods 1-2 b													28-35 days (Follow-Up)	Early Termination/Discontinuation	
		Day -1	Day 1														
Days Relative to Day 1	Days -28 to -2	0	0.5	1	1.5	2	2.5	3	4	6	8	12	16	24	48		
Hours After Dose																	
COVID-19 testing o	X	X u															
Ritonavir administration b		X										X					
PF-07321332/ritonavir administration q			X														
PK Blood Sampling for PF-07321332 r			X	X	X	X	X	X	X	X	X	X	X	X	X	X	X
CCI																	

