### **5.3.3. Activity**

- Participants will abstain from strenuous exercise (eg, heavy lifting, weight training, calisthenics, aerobics) for at least 48 hours prior to each blood collection for clinical laboratory tests. Walking at a normal pace will be permitted;
- In order to standardize the conditions on PK sampling days, participants will be required to refrain from lying down (except when required for BP, respiratory rate, pulse rate, and ECG measurements), eating, and drinking beverages other than water during the first 4 hours after PF-07321332/ritonavir dosing;
- Participants will be confined to the procedure room for the first 4 hours after dosing on Day 1, except to use the bathroom. After this, participants may be ambulatory but should not engage in strenuous activities.

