### 6.1.1. Administration

Investigational products will be administered orally and according to the conditions described in the [SoA](#) section and Protocol Section [5.3.1 Meals and Dietary Restrictions](#).

For **fasted** period (Sequence 1, Period 1 and Sequence 2, Period 2):

- On Day -1, 12 hours prior to dosing of PF-07321332, participants will receive a 100 mg ritonavir tablet (as 1 × 100 mg) with approximately 240 mL ambient temperature water. On Day 1, following an overnight fast of at least 10 hours, the participants will receive 300 mg PF-07321332 (as 2 × 150 mg tablets) with 100 mg ritonavir (as 1 × 100 mg tablet) administered orally at approximately 08:00 hours (plus or minus 2 hours) without breakfast/standard meal on Day 1. 12 hours after dosing of PF-07321332, participants will receive a 100 mg ritonavir tablet (as 1 × 100 mg) with approximately 240 mL ambient temperature water.

For **fed** periods (Sequence 2, Period 1 and Sequence 1, Period 2):

- On Day -1, 12 hours prior to dosing of PF-07321332, participants will receive a 100 mg ritonavir tablet (as 1 × 100 mg) with approximately 240 mL ambient temperature water. On Day 1, following an overnight fast of at least 10 hours, participants will receive breakfast approximately 30 minutes prior to dosing which is to be completed within approximately 20 minutes as outlined in Section [5.3.1 \(Meals and Dietary Restrictions\)](#). The participants will then receive 300 mg PF-07321332 (as 2 × 150 mg tablets) with 100 mg ritonavir (as 1 × 100 mg tablet) administered orally at approximately 08:00 hours (plus or minus 2 hours). 12 hours after dosing of PF-07321332, participants will receive a 100 mg ritonavir tablet (as 1 × 100 mg) with approximately 240 mL ambient temperature water.

For **all** periods:

- PF-07321332 and ritonavir will be dosed simultaneously (within no more than 5 minutes of each other). Investigator site personnel will administer study intervention during each period with ambient temperature water to a total volume of approximately 240 mL. Participants will swallow all tablet formulations whole, and will not manipulate or chew the study intervention prior to swallowing.
- In order to standardize the conditions on PK sampling days, all participants will be required to refrain from lying down (except when required for BP, pulse rate, and ECG measurements), eating, and drinking beverages other than water during the first 4 hours after dosing.

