### **6.4. Study Intervention Compliance**

When participants are dosed at the site, they will receive study intervention directly from the investigator or designee, under medical supervision. The date and time of each dose administered in the clinic will be recorded in the source documents and recorded in the CRF. The dose of study intervention and study participant identification will be confirmed at the time of dosing by a member of the study site staff other than the person administering the study intervention. Study site personnel will examine each participant's mouth to ensure that the study intervention was ingested.

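### Protocol 5.3.1 leaves water free around dosing in fed periods but, apart from the common dosing water, bars it for an hour either side in fasted periods, so any water effect is counted in the fed/fasted ratio

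*Protocol*

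**What the plan says.** Protocol 5.3.1 (Meals and Dietary Restrictions) sets the water rule separately for each condition.

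- **Fed periods (Treatment B, Test):** "There are no water restrictions prior to and after dosing". The sentence closes a bullet that is limited to the fed periods.
- **Fasted periods (Treatment A, Reference):** "water is permitted until 1 hour prior to study intervention administration. Water may be consumed without restriction beginning 1 hour after dosing".

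Three further fluid rules apply in both conditions:

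- The 10-hour fast before the predose PK sample exempts water (5.3.1).
- Dosing water is the same throughout: "Investigator site personnel will administer study intervention during each period with ambient temperature water to a total volume of approximately 240 mL" (6.1.1).
- After dosing, participants must refrain from "drinking beverages other than water during the first 4 hours after PF-07321332/ritonavir dosing" (5.3.3, repeated in substance in 6.1.1). Water is outside that bar.

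Section 6.1.1 states "Investigational products will be administered orally and according to the conditions described in the" Schedule of Activities and Section 5.3.1, so the rules in 5.3.1 are the ones a site would follow. The only rationale in the fed bullet concerns the choice of meal and does not mention water.

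The primary objective (Protocol 3, SAP 2.1) is the effect of a high-fat meal on exposure. It is estimated as the Test/Reference ratio of adjusted geometric means with a 90% CI, from a mixed model with sequence, period and treatment as fixed effects and participant within sequence as a random effect (Protocol 9.3.1.2, SAP 6.1).

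**The concern.** A crossover food-effect study attributes the fed/fasted difference to the meal, which requires other conditions around dosing to be the same in both periods. The protocol takes that aim seriously elsewhere. It fixes the dosing water, bars other beverages for 4 hours in order to standardise PK sampling days, and restricts water on both sides of the fasted dose. In fed periods it leaves water open.

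If participants drink more water near the fed dose than near the fasted dose, and if that alters early absorption, the ratio reflects both the meal and the water. The 0.5-hour PK sample falls inside the window where the rules differ and the 1-hour sample falls at its edge, so Cmax is exposed to this as well as AUC. What is at stake is how exactly the ratio can be described as a meal effect. Protocol 2.1 intends the results to inform pre- and post-marketing use.

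**Working it through.** The plan states no figure for a water effect, so there is none to reproduce. The check covers the window, the overlap with treatment, and how an effect would pass into the estimate.

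**1. The window (5.3.1).** Times are minutes relative to dosing.

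- Fasted bar on water: −60 to +60 = 120 min. The common dosing water of about 240 mL at time 0 is the exception.
- Fed breakfast: starts at about −30 and lasts about 20 min, so about −30 to −10.
- Difference in access outside breakfast: (60 − 20) + 60 = 100 min.
- Share of the common 4-hour beverage rule during which water access still differs: 60 / 240 = 25%.

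These figures describe the rule. They do not measure a bias in Cmax or AUC.

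**2. Overlap with treatment (sequences from Protocol Table 1, rules from 5.3.1).**

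| Cell | Treatment | Water from −60 to +60 min |
|---|---|---|
| Sequence 1, Period 1 | A, fasted | barred, except dosing water |
| Sequence 1, Period 2 | B, fed | free |
| Sequence 2, Period 1 | B, fed | free |
| Sequence 2, Period 2 | A, fasted | barred, except dosing water |

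The water rule matches treatment in 4 of 4 cells.

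**3. Separability.** Write F = 1 in fed periods and W = 1 where water is free. On the log scale:

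log(parameter) = participant + period + τF + ωW

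Since W = F throughout, this becomes participant + period + (τ + ω)F. Only the sum can be estimated, and the reported ratio is exp(τ) × exp(ω).

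A numerical check used 12 participants, 6 per sequence, with 12 × 2 = 24 participant-periods. The design matrix with participant, period and treatment columns (12 + 1 + 1) has rank 14. Adding the water column leaves the rank at 14, and the correlation between F and W is 1. The water rule is completely aliased with treatment.

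**4. Pass-through under assumed effects.** The water multipliers and the meal ratio of 1.20 are assumptions chosen to show the mechanism. The documents supply neither.

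| Assumed water multiplier | Ratio if true meal ratio is 1.00 | Ratio if true meal ratio is 1.20 |
|---|---|---|
| 0.90 | 0.90 | 1.20 × 0.90 = 1.08 |
| 0.95 | 0.95 | 1.20 × 0.95 = 1.14 |
| 1.00 | 1.00 | 1.20 |
| 1.05 | 1.05 | 1.20 × 1.05 = 1.26 |
| 1.10 | 1.10 | 1.20 × 1.10 = 1.32 |

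An effect passes one for one into the ratio. If water has no effect, nothing is distorted.

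**5. Does any other rule equalise water?** No. The fast exempts water, the dosing water is common but does not limit further drinking in fed periods, and the 4-hour rule covers only other beverages.

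**The case against.** The strongest reply is that fed and fasted are whole conditions. The treatments are defined that way, the SAP labels its outputs that way, and 6.1.1 ties both to 5.3.1, so the water rule is already part of what is compared. This stands to the extent that the ratio is a valid contrast of the two conditions as specified. It does not settle the matter, because the primary objective names the high-fat meal. Nothing in the documents makes water drunk freely up to an hour after dosing part of that meal.

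A second reply is that the aliasing is true by construction, since every feature of the fed condition is aliased with treatment, including fluid served at breakfast. That is correct, and the rank check does not show that an effect exists. The water rule differs from the meal in that it can be made common to both conditions without altering the meal.

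Third, extra water is permitted and not required, the dosing water is common, and no hypothesis test or decision rule depends on the ratio (Protocol 9.1, SAP 5.1). All of this stands and keeps the point minor.

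A reader might also infer that the two bullets contradict each other. They do not: each is limited to its own periods, and a site can follow both. Nor do the documents show that water intake will go unrecorded. Section 6.4 asks for dose times ("The date and time of each dose administered in the clinic will be recorded in the source documents and recorded in the CRF") and the protocol text requests no water record. However, the Schedule of Activities describes itself as an overview ("The SoA table provides an overview of the protocol visits and procedures"), one of its rows is redacted, and no readable row covers meals either. It says little about what the site will record.

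**Conclusion.** The point holds as a minor, avoidable confound. The water rule around dosing differs by treatment without a stated reason, no other section evens it out, and any resulting effect on early absorption is included in the fed/fasted Cmax and AUC ratios inseparably from the meal effect.

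The documents give no size or direction. The effect is probably small. A distortion requires two things that the documents do not establish: that participants actually drink more water near the fed dose, and that this changes absorption of PF-07321332. The tempting stronger conclusion, that the ratio is biased or invalid, is therefore unsupported. The consequence is for interpretation only.

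**What to change.** Align the two bullets in Protocol 5.3.1 so that one common water rule around dosing applies in fed and fasted periods. The approximately 240 mL dosing water stays as it is, and any fluid served as part of the test breakfast remains part of the meal condition. Which common rule to adopt is for the sponsor to decide.

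The change is one or two sentences and affects neither the sample size nor the analysis. The downside is a minor change in water access for participants in one condition. A common rule equalises permitted access, not actual intake, so some difference in drinking could remain.
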